12. COSTS AND PAYMENTS

12.1. Research Study Costs:

Screening and clinical assessment of the patient prior to the procedure will be no different than what typically occurs prior to conventional radiation therapy. Therefore, a patient's insurance will be billed for all tests and imaging associated with this evaluation. The cost of the procedure itself will be billed to the patient's insurance company under an appropriate code. This will include all operative, facility-based and hospital-based charges. Follow-up assessment also is no different than what typically occurs following a conventional radiotherapy and treatment for this population of patients. Therefore, the patient's insurance will be billed for all tests and imaging associated with the follow-up visits.

13. Research Study Payments:

There will be no financial reimbursement to the patient for participation in this evaluation.

14. APPENDICES

Appendix I: Sample Patient Consent Form

Appendix II: Performance Status Scales

ECOG PERFORMANCE SCALE

- 0 Fully active, able to carry on all predisease activities without restriction (*Karnofsky 90-100*).
- 1 Restricted in physically strenuous activity but ambulatory and able to carry out work of a light or sedentary nature. For example, light housework, office work (*Karnofsky 70-80*).
- 2 Ambulatory and capable of all self-care but unable to carry out any work activities. Up and about more than 50% of waking hours (*Karnofsky 50-60*).
- 3 Capable of only limited self-care, confined to bed or chair 50% or more of waking hours (*Karnofsky 30-40*).
- 4 Completely disabled. Cannot carry on any self-care. Totally confined to bed or chair (*Karnofsky 10-20*).

Appendix III: AJCC STAGING SYSTEM, 7TH EDITION, PROSTATE

Primary Tumor, Clinical (T)

TX Primary tumor cannot be assessed

T0 No evidence of primary tumor

T1 Clinically inapparent tumor not palpable or visible by imaging

 T1a Tumor incidental histologic finding in 5% or less of tissue resected

 T1b Tumor incidental histologic finding in more than 5% of tissue resected

 T1c Tumor identified by needle biopsy (*e.g., because of elevated PSA*)

T2 Tumor confined with prostate*

 T2a Tumor involves less than ½ of one lobe

 T2b Tumors involves greater than ½ of one lobe but < 2 lobes

 T2c Tumor involves both lobes

T3 Tumor extends through prostate capsule**

 T3a Extracapsular extension (*unilateral or bilateral*)

 T3b Tumor involves the seminal vesicle(s)

T4 Tumor is fixed or invades adjacent structures other than the seminal vesicles: bladder neck, external sphincter, rectum, levator muscles and/ or pelvic wall

*Note: Tumor found in one or both lobes by needle biopsy, but not palpable or reliably visible by imaging, is classified as T1c

**Note: Invasion into the prostatic apex or into (*but not beyond*) the prostatic capsule is not classified as T3, but as T2.

Regional Lymph Nodes (N)

Clinical NX Regional lymph nodes cannot be assessed

 N0 No regional lymph node metastasis

 N1 Metastasis in regional lymph node or nodes

Pathologic pNX Regional nodes not sampled

 pN0 No positive regional nodes

 pN1 Metastases in regional node(s)

*Distant Metastasis (M)**

MX Presence of distant metastasis cannot be assessed (not evaluated by any modality)

M0 No distant metastasis

M1 Distant metastasis

 M1a Nonregional lymph node(s)

 M1b Bone(s)

 M1c Other site(s) with or without bone disease

*Note: When more than one site of metastasis is present, the most advanced category is used; pM1c is most advanced.

Appendix IV: Data Collection Documents

Appendix V: NCI Common toxicity criteria/RTOG/EORTC:

Refer to:

http://ctep.cancer.gov/protocolDevelopment/electronic_applications/docs/ctcaeV3.pdf

Appendix VI: AUA, EPIC, SHIM Questionnaires

American Urological Association (AUA) symptom index: was developed to help men determine how bothersome their urinary symptoms are and to check the effectiveness of treatment.^{vi} This questionnaire has also been adopted worldwide and is known as the International Prostate Symptom Score (IPSS). It is sometimes seen with a Quality of Life Scale at the end of the questionnaire.

Name: _____

Today's date: _____

(Circle one number on each line)	Almost never	Less than 1 time in 5	Less than half the time	About half the time	More than half the time	Almost always
Over the past month or so, how often have you had a sensation of not emptying your bladder completely after you finished urinating?	0	1	2	3	4	5
Over the past month or so, how often have you had to urinate again less than two hours after you finished urinating?	0	1	2	3	4	5
Over the past month or so, how often have you found you stopped and started again several times when you urinated?	0	1	2	3	4	5
Over the past month or so, how often have you found it difficult to postpone urination?	0	1	2	3	4	5
Over the past month or so, how often have you had a weak urinary stream?	0	1	2	3	4	5
Over the past month or so, how often have you had to push or strain to begin urination?	0	1	2	3	4	5
	None	1 time	2 times	3 times	4 times	5 or more times
Over the past month, how many times did you most typically get up to urinate from the time you went to bed at night until the time you got up in the morning?	0	1	2	3	4	5

EPIC-26
The Expanded Prostate Cancer Index Composite
Short Form

This questionnaire is designed to measure Quality of Life issues in patients with Prostate cancer. To help us get the most accurate measurement, it is important that you answer all questions honestly and completely.

Remember, as with all medical records, information contained within this survey will remain strictly confidential.

Today's Date (please enter date when survey completed): Month _____ Day _____ Year _____

Name (optional): _____

Date of Birth (optional): Month _____ Day _____ Year _____

1. Over the past 4 weeks, how often have you leaked urine?

More than once a day..... 1

About once a day..... 2

More than once a week..... 3

(Circle one number)

23/

About once a week..... 4

Rarely or never..... 5

2. Which of the following best describes your urinary control during the last 4 weeks?

No urinary control whatsoever..... 1

Frequent dribbling..... 2 (Circle one number)

26/

Occasional dribbling..... 3

Total control..... 4

3. How many pads or adult diapers per day did you usually use to control leakage
during the last 4 weeks?

None 0

1 pad per day..... 1

2 pads per day..... 2 (Circle one number)

27/

3 or more pads per day..... 3

4. How big a problem, if any, has each of the following been for you during the last 4 weeks?

(Circle one number on each line)

	No Problem	Very Small Problem	Small Problem	Moderate Problem	Big Problem	
a. Dripping or leaking urine	0	1	2	3	4	28/
b. Pain or burning on urination.....	0	1	2	3	4	29/
c. Bleeding with urination.....	0	1	2	3	4	30/
d. Weak urine stream or incomplete emptying.....	0	1	2	3	4	31/
e. Need to urinate frequently during the day.....	0	1	2	3	4	33/

5. Overall, how big a problem has your urinary function been for you during the last 4 weeks?

No problem..... 1

Very small problem..... 2

Small problem..... 3

(Circle one number)

34/

Moderate problem..... 4

Big problem..... 5

6. How big a problem, if any, has each of the following been for you? (Circle one number on each line)

	No Problem	Very Small Problem	Small Problem	Moderate Problem	Big Problem	
a. Urgency to have a bowel movement	0	1	2	3	4	49/
b. Increased frequency of bowel movements.....	0	1	2	3	4	50/
c. Losing control of your stools.....	0	1	2	3	4	52/
d. Bloody stools	0	1	2	3	4	53/
e. Abdominal/ Pelvic/Rectal pain...	0	1	2	3	4	54/

7. Overall, how big a problem have your bowel habits been for you **during the last 4 weeks?**

No problem.....	1					
Very small problem.....	2					
Small problem.....	3					
Moderate problem.....	4					
Big problem.....	5					

(Circle one number) 55/

8. How would you rate each of the following **during the last 4 weeks?** (Circle one number on each line)

	Very Poor to None	Poor	Fair	Good	Very Good	
a. Your ability to have an erection?.....	1	2	3	4	5	57/
b. Your ability to reach orgasm (climax)?.....	1	2	3	4	5	58/

9. How would you describe the usual **QUALITY** of your erections **during the last 4 weeks?**

None at all.....	1					
Not firm enough for any sexual activity.....	2					
Firm enough for masturbation and foreplay only.....	3					
Firm enough for intercourse.....	4					

10. How would you describe the **FREQUENCY** of your erections **during the last 4 weeks?**

I NEVER had an erection when I wanted one.....	1					
I had an erection LESS THAN HALF the time I wanted one.....	2					
I had an erection ABOUT HALF the time I wanted one	3					
I had an erection MORE THAN HALF the time I wanted one.....	4					
I had an erection WHENEVER I wanted one.....	5					

11. Overall, how would you rate your ability to function sexually during the last 4 weeks?

Very poor.....	1	
Poor.....	2	
Fair.....	3	(Circle one number)
Good.....	4	
Very good.....	5	

64/

12. Overall, how big a problem has your sexual function or lack of sexual function been for you during the last 4 weeks?

No problem.....	1	
Very small problem.....	2	
Small problem.....	3	(Circle one number)
Moderate problem.....	4	
Big problem.....	5	

68/

13. How big a problem during the last 4 weeks, if any, has each of the following been for you?
(Circle one number on each line)

	No Problem	Very Small Problem	Small Problem	Moderate Problem	Big Problem	
a. Hot flashes.....	0	1	2	3	4	74/
b. Breast tenderness/enlargement..	0	1	2	3	4	75/
c. Feeling depressed.....	0	1	2	3	4	77/
d. Lack of energy.....	0	1	2	3	4	78/
e. Change in body weight.....	0	1	2	3	4	79/

THANK YOU VERY MUCH!!

SEXUAL HEALTH INVENTORY FOR MEN (SHIM)

PATIENT NAME: _____ TODAY'S DATE: _____

PATIENT INSTRUCTIONS

Sexual health is an important part of an individual's overall physical and emotional well-being. Erectile dysfunction, also known as impotence, is one type of very common medical condition affecting sexual health. Fortunately, there are many different treatment options for erectile dysfunction. This questionnaire is designed to help you and your doctor identify if you may be experiencing erectile dysfunction. If you are, you may choose to discuss treatment options with your doctor.

Each question has several possible responses. Circle the number of the response that **best describes** your own situation. Please be sure that you select one and only one response for **each question**.

OVER THE PAST 6 MONTHS:

1. How do you rate your confidence that you could get and keep an erection?		VERY LOW	LOW	MODERATE	HIGH	VERY HIGH
		1	2	3	4	5
2. When you had erections with sexual stimulation, how often were your erections hard enough for penetration (entering your partner)?	NO SEXUAL ACTIVITY	ALMOST NEVER OR NEVER	A FEW TIMES (MUCH LESS THAN HALF THE TIME)	SOMETIMES (ABOUT HALF THE TIME)	MOST TIMES (MUCH MORE THAN, HALF THE TIME)	ALMOST ALWAYS OR ALWAYS
	0	1	2	3	4	5

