8.5. CYBERKNIFE® TREATMENT DELIVERY

8.5.1. The prescribed PTV dose shall be given using the CyberKnife®

8.5.2. Bowel/bladder preparation:

8.5.2.1. The rectum will be emptied of its contents by use of one or more Fleets enemas prior to the planning CT and MRI scans.

8.5.2.2. To improve comfort and minimize inconvenience to the patient, if possible, the CT and MRI planning studies will be done consecutively.

8.5.3. Treatment should be completed within 7 days.

8.5.4. At least three fiducials should be identified for each treatment. If fewer than three fiducials can be tracked, then additional fiducials will be placed, and the patient replanned. Every effort will be made to treat using rotational corrections. The treatment system will be set to record rotations on the treatment printout. On a given treatment, if rotational corrections are not possible, treatment may continue, with rotational deltas recorded, as long as these remain below 2 degrees. For subsequent treatments, diet changes or additional bowel preparations will be made, and/or rectal tube placed, and treatment shall be attempted using rotational corrections. If treatment proceeds without rotational corrections, the therapist shall inform the attending radiation oncologist, and record the duration of treatment performed without rotations.

8.5.5. On the day of the CyberKnife® treatment, the patient will be taken into the CyberKnife® system treatment room, set up in their respective immobilization devices and positioned on the CyberKnife® couch. X-rays will be taken with the CyberKnife® system to ensure that the tumor is aligned in a manner consistent with the position in which the treatment plan CT image was taken. Target movement is expected to require imaging every 1-3 nodes, per the discretion of the attending physician, and in no situation should imaging occur less frequently than every 5 nodes. Fiducial locations in the images will be extracted and compared to the fiducial locations in the CT scans to estimate target movements. The following planning and treatment information shall be recorded for every plan and fraction delivered: set-up

time required, number of nodes treated, number of nodes treated with rotational corrections, number of nodes imaged, and total treatment time. This data will be collected onto Case Report Forms.

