9. PATIENT ASSESSMENTS AND TOXICITY

Assessment	Pre-entry		Follow-up (# of months from last radiation therapy treatment)									
			1	3	6	12	18	24	30	36	48	60
History	X			X	X	X	X	X	X	X	X	X
Physical exam (DRE)	X			X	X	X	X	X	X	X	X	X
ECOG Performance Scale	X			X	X	X	X	X	X	X	X	X
Prostate Biopsy & Gleason score	X											
PSA	X			X	X	X	X	X	X	X	X	X
Prostate volume assessment	X											
CBC, platelets	X											
BUN, creatinine	X											
Toxicity evaluation	X			X	X	X	X	X	X	X	X	X
AUA score	X			X	X	X	X	X	X	X	X	X
EPIC-26 Questionnaire	X			X	X	X	X	X	X	X	X	X
SHIM Questionnaire	X			X	X	X	X	X	X	X	X	X

Follow up evaluations may be performed +/- 30 days

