9.1. EVALUATION DURING TREATMENT & FOLLOWING TREATMENT

9.1.1. PRE-ENTRY ASSESSMENT: see section 4.7.

9.1.2. Stereotactic radiosurgery is an outpatient procedure. Patient management immediately after the procedure will follow routine patient care guidelines as determined by the physician. Subjects will be provided instructions on who to call with specific contact information, in the event they experience any untoward effects following treatment. In the event a subject experiences any untoward effects following CyberKnife® treatment, information specific to the patient's condition and symptoms, treatment intervention required, and hospital stay and course will be recorded for purposes of clinical evaluation.

9.1.3. ASSESSMENTS FOLLOWING TREATMENT: At 1 month following last radiation treatment, patients will be assessed for

acute toxicity, and will fill out AUA form, EPIC-26 and SHIM. At month 3, every 6 months from year 1-3 (months 6, 12, 18 and 24, 30 and 36) and at year 4 and 5, AUA, EPIC-26 and SHIM will be administered, and an H&P with DRE and toxicity evaluation will be completed. Examination and studies may be done at outside facility.

9.1.4. Recommended: at the time of biochemical failure, or when the patient develops signs of symptoms suggesting metastatic disease, it is at the physician's discretion to perform a prostate biopsy or imaging studies.

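### SHIM asks about six months, so its month-1 and month-3 scores mix function before, during and after radiation and cannot be read as post-treatment function

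*Combined protocol and SAP*

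**What the plan says.** The SHIM form in Appendix VI is headed "OVER THE PAST 6 MONTHS". Section 9.1.3 sets the first assessment: "At 1 month following last radiation treatment, patients will be assessed for" "acute toxicity, and will fill out AUA form, EPIC-26 and SHIM". It then repeats the three questionnaires at month 3, six-monthly to month 36, and finally "at year 4 and 5, AUA, EPIC-26 and SHIM will be administered".

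The Section 9 schedule table counts visits as "Follow-up (# of months from last radiation therapy treatment" and adds "Follow up evaluations may be performed +/- 30 days". As far as its layout can be read, each follow-up row, SHIM included, has nine marks for ten columns, starting at month 3. Month 1 therefore appears blank, which disagrees with Section 9.1.3. The layout may have been damaged in extraction.

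The other two instruments look back about a month: the AUA index over roughly the past month, and the EPIC-26 sexual items (questions 8 to 12) over the last 4 weeks. Section 11.1 says only that quality of life will be summarised descriptively. It does not say which instrument carries sexual function at which visit, or how an early SHIM score is to be read.

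**The concern.** A score filed under month 1 or month 3 will be taken as function at that time after treatment. With a six-month recall it cannot be, because the question itself reaches back past the end of radiation.

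This matters because sexual function is part of the case for the device. Section 1.13 argues for an advantage over HDR brachytherapy in erectile function, and Section 12.3 lists less sexual toxicity among the possible benefits. The end of Section 1 says questionnaire results will be compared with published results for other treatments. An early SHIM change that includes earlier function could make such a comparison look more favourable than it is. The plan gives the reader no warning of this.

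**Working it through.** The plan states no figure for this point, so there is none to reproduce. The check is recall-window arithmetic.

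**Inputs**
- Recall R = 6 months (SHIM form, Appendix VI).
- Visit time t = 1, 3 or 6 months from the last radiation treatment (Sections 9 and 9.1.3), with a 30-day allowance either way.
- Monotherapy course of 7 to 10 days: Section 8.5.3 says "Treatment should be completed within 7 days", and Section 8.4.4.1 allows just under 10 days.
- Boost plus IMRT: the documents give no total duration. Assumed range: 5 to 9 weeks (35 to 63 days).
- One month = 30.4 days.

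**Formulas**
- Share after the end of radiation = min(t, R)/R.
- Share before the end of radiation = 1 − that value.
- Share during the course = min(R − t, course length)/R.
- Share before the course starts = the remainder.

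**Before the end of radiation, visits on time**
- Month 1: (6 − 1)/6 = 83%.
- Month 3: (6 − 3)/6 = 50%.
- Month 6: (6 − 6)/6 = 0%.

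**Split of the window, visits on time**

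Example for a 7-day course: 7/30.4 = 0.23 months, and 0.23/6 = 4%. At month 1 this leaves 83% − 4% = 79% before treatment began. For an assumed 35-day course: 35/30.4 = 1.15 months, 1.15/6 = 19%, leaving 64%.

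| Visit | Course | After | During | Before start |
|---|---|---|---|---|
| Month 1 | Monotherapy, 7–10 days | 17% | 4–5% | 79–78% |
| Month 1 | Boost + IMRT, assumed 5–9 weeks | 17% | 19–35% | 64–49% |
| Month 3 | Monotherapy, 7–10 days | 50% | 4–5% | 46–45% |
| Month 3 | Boost + IMRT, assumed 5–9 weeks | 50% | 19–35% | 31–15% |
| Month 6 | Either | 100% | 0% | 0% |

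Rows may not sum to exactly 100% because of rounding.

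**Effect of the visit allowance** (30/30.4 = 0.99 months)
- Month 1: the share after radiation runs from 0% (visit 30 days early) to 33% (30 days late).
- Month 3: it runs from 34% to 66%. The share before treatment started is 28–63% for monotherapy and about 0–47% for boost.
- Month 6: a visit 30 days early still has 16% of its window before the end of radiation.

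**What this could do to a change score.** Assume that men average evenly over six months and that function drops by D at the end of radiation and stays there. The measured change would then be D/6 (17% of D) at month 1 and D/2 at month 3. This illustrates the mechanism; it is not an estimate.

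**Comparison with EPIC-26.** Four weeks is 28 days. An on-time month-1 visit falls 30.4 days after the last treatment, so the whole EPIC-26 window is post-treatment, with 30.4 − 28 = 2.4 days to spare. A month-3 visit held 30 days early is still 91.2 − 30 = 61.2 days out, well clear of 28.

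**The case against.** A reader might infer that both early SHIM scores mostly describe pre-treatment function and therefore understate sexual harm. The documents do not support that.

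- At an on-time month-3 visit half the window is after radiation, so less than half can be before treatment. In boost patients part of the remainder is the radiation course itself.
- The month-1 figure applies only if that visit includes SHIM. Section 9.1.3 says it does, but the table appears to say otherwise.
- The direction of any bias is not established. Section 8.1 strongly recommends androgen deprivation in both risk groups, and the eligibility checklist anticipates that it may already have started. Where it has, the earlier part of the window is not clean baseline function.
- Even averaging over six months is an assumption. The first SHIM item asks about present confidence and may not average over time at all.

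It can also be said that EPIC-26 already covers the early visits, that no test or threshold depends on SHIM, and that giving a validated form unaltered at every visit is a reasonable choice.

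All of this limits the point without removing it. Uncertain direction makes an early SHIM score harder to attribute to radiation, not easier. Collecting EPIC-26 alongside it makes the remedy cheap, but the plan has no rule that makes EPIC-26 the measure to lead with. The objection to altering the form is met by leaving the form as it is and changing only how the early scores are reported.

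**Conclusion.** The point holds as a minor one about interpretation. About 83% of the SHIM window at month 1 (if SHIM is given then) and about 50% at an on-time month 3 precedes the end of radiation, counting pre-treatment and on-treatment time together. These shares follow from the form and the schedule alone. Only the split between pre-treatment and on-treatment time in boost patients rests on an assumed course length.

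The scores should not be presented as post-treatment function. Dilution of the early change is plausible if recall averages over the window and function falls after radiation. Neither its size nor its direction can be fixed from the documents, so a claim that harm is understated goes too far. SHIM windows at on-time visits from month 6 lie wholly after treatment, and the biochemical disease-free survival endpoint is unaffected.

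**What to change.** Add to Section 11.1 that:
- the EPIC-26 sexual domain is the sexual-function measure at months 1 and 3;
- SHIM scores at those visits are flagged as covering a period before, during and after radiation;
- SHIM change from pre-entry is interpreted only from month 6 onward.

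Report actual visit dates with these results, since a month-6 visit held early, or a month-1 EPIC-26 completed more than about two days early, still reaches back into treatment. Reconcile Section 9.1.3 with the Section 9 table on whether the questionnaires are given at month 1.

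The cost is that two descriptive SHIM time points carry less weight. No new data, altered form or change in sample size is needed.
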